8.3 Expected Adverse Events

8.3.1 Surgery

Atelectasis, lung infection, pneumonitis, dyspnea, adult respiratory distress syndrome, pleural infection, thromboembolic event, myocardial infarction, ventricular arrhythmia, arterial injury, venous injury, wound infection, bronchopleural fistula, postoperative hemorrhage, sepsis, recurrent laryngeal nerve palsy, intraoperative respiratory injury, postoperative thoracic procedure complication, changes in pulmonary function tests (e.g., forced expiratory volume (FEV1) decreased; carbon monoxide diffusion capacity (DLCO) decreased; vital capacity abnormal).

8.3.2 Brachytherapy

Lung infection, pneumonitis, dyspnea, adult respiratory distress syndrome, pleural infection, bronchopleural fistula.

8.3.3 Z4032 Adverse Event Data

In addition to the risks listed above, the most common (i.e., occurring in four or more instances) Grade 3 or higher events identified in the Z4032 SR and SR + BR arms include (in CTCAE V3 terms): hemorrhage – surgical, infection (pneumonia) with Grade 0-2 ANC, infection (pneumonia) with unknown ANC, urinary tract infection, hypoxia, atrial fibrillation, hypotension, dehydration.

8.3.4 Stereotactic Body Radiation Therapy

Pneumonitis, atelectasis, bronchial obstruction, bronchial stricture, bronchopleural fistula, chest wall pain, fracture, changes in pulmonary function tests (e.g., forced expiratory volume (FEV1) decreased; carbon monoxide diffusion capacity (DLCO) decreased; vital capacity abnormal), pulmonary fibrosis, burn, dermatitis radiation, alopecia, cough (may be productive), dyspnea, fever, fatigue, pericarditis, pericardial effusion, chest pain – cardiac, palpitations, heart failure, myocardial infarction, paresthesias, generalized muscle weakness, esophagitis, dysphagia, aortic or arterial injury, hemoptysis, pain of skin.

8.4 RTOG Pulmonary Function Test Toxicity Scale

Changes in pulmonary function tests (FEV-1, FVC, DLCO, etc) for all patients will be graded using the RTOG Pulmonary Function Test Toxicity Scale. The RTOG Pulmonary Function Test Toxicity Scale is preferred for this protocol because it accounts for baseline abnormalities in pulmonary function which will be common based on the protocol's eligibility criteria.

Changes that occur after therapy will be referenced to baseline for a given patient, which will be abnormal for most patients. The RTOG scale defines a proportional decline from the baseline. Grade 1 toxicity will be a decline from baseline to a level 0.90 times the baseline, grade 2 will be a decline to a level 0.75 of baseline, grade 3 will be a decline to a level 0.5 of baseline, grade 4 will be a decline to a level 0.25 of baseline, and grade 5 will be death. This scheme is depicted in the table below and graphically represented

in the figure below. Both arms of this trial will utilize this alternate pulmonary function toxicity scale rather than the CTCAE for grading and reporting changes in PFTs.

As an example, a patient who enters the study with a percent predicted DLCO of 55% who experiences a post treatment decline to a percent predicted DLCO of 40% would have a grade 4 event in the original CTCAE version 4 criteria; however, under this modified PFT toxicity classification for patients with abnormal baseline, his decline would constitute a decrease to 0.72 of the baseline value which is between 0.75 and 0.5 or a grade 2 event.

RTOG Pulmonary Function Test Toxicity Scale										
	Grade									
Adverse Event	1	2	3	4	5					
FEV-1 Decline	0.90-0.75	<0.75-0.50	<0.50-0.25	<0.25	Death					
	times the	times the	times the	times the						
	patient's	patient's	patient's	patient's						
	baseline value	baseline value	baseline value	baseline value						
Forced Vital	0.90-0.75	<0.75-0.50	<0.50-0.25	<0.25	Death					
Capacity	times the	times the	times the	times the						
Decline	patient's	patient's	patient's	patient's						
	baseline value	baseline value	baseline value	baseline value						
DLCO Decline	0.90-0.75	<0.75-0.50	< 0.50-0.25	< 0.25	Death					
	times the	times the	times the	times the						
	patient's	patient's	patient's	patient's						
	baseline value	baseline value	baseline value	baseline value						

PFT(FEV-1, FVC, DLCO) Decline

9 Data Considerations

All CRFs are available on the Z4099 page of the ACOSOG web site at http://www.acosog.org or under the Protocols tab of the CTSU website at https://www.ctsu.org.

9.1 Case Report Form Completion and Submission Guidelines

This study will utilize Medidata Rave® for remote data capture (RDC) of all data.

To receive Rave system access, sites must complete the ACOSOG Roster Personnel Information Form (available at https://ncctg.mayo.edu/acosog/roster-rdc-access.dot) and fax the completed form to the number provided. The ACOSOG Roster Personnel Form is required for each person responsible for data entry and should be submitted prior to the first patient registration.

Allied Health Professionals/CRAs at participating sites will receive two emails: 1) an email invitation from [contact] to set up their user id and password; and 2) an email which provides additional instructions on account setup. Once an account is established, eLearning modules will be provided for Rave RDC instruction. All modules must be completed prior to gaining access to data entry. Further training opportunities will be communicated through the web site.

The Rave system can be accessed through the iMedidata portal at https://login.imedidata.com.

Contact the QA Specialist with all questions about Medidata Rave.

10 Statistical Considerations

10.1 Study Design

This is a randomized Phase III non-inferiority trial design comparing the control arm, sublobar resection (SR) with or without brachytherapy, to the experimental arm, stereotactic body radiation (SBRT) in operably high-risk patients with stage I non-small cell lung cancer (NSCLC).

10.1.1 Primary Endpoint

The primary aim of this Phase III trial is to test the hypothesis that SBRT for operable high-risk patients with stage I NSCLC is not inferior to SR with or without brachytherapy. The primary endpoint is overall survival defined as the time from randomization until death from any cause. All patients will be followed for the primary endpoint for a minimum of 5 years.

Based on historical data, we expect the three-year survival rate for SR (control group) to be 80%. We will accept a 10% decrement from the three-year survival rate for SR arm of the study to be considered noninferior. Rationale for the up to 10% decrement in three-year survival for the SBRT arm is that SBRT is expected to be significantly better tolerated (i.e. have a significantly better adverse event profile) than SR. One line of evidence to support this expectation is that it has been established that stage I patients who are medically inoperable (unable to tolerate any form of lung resection) can tolerate SBRT because it is less invasive and has a lower adverse event profile compared to SR. Hence, in this high-risk population (patient who can tolerate SR but not the first line surgery of lobar resection), SBRT will likely have a considerably better adverse event profile (and QOL profile) than SR. There is also some evidence in the literature that supports a significantly improved adverse event profile of SBRT compared to SR in this population. Specifically, a large study of 182 patients undergoing segmental resection demonstrated complications in 32.4% of patients [103]. This compares to a recent report of SBRT that reported a 10% rate of grade 3+ toxicities [19]. It is difficult to compare these values because they did not use the same adverse event grading scale. However, this potentially indicates that the expected grade 3+ adverse event rate for SRBT might be half that for SR. Given this, it is felt that an inferiority margin of at most 10% in three year survival is balanced by a anticipated decrease in grade 3+ adverse events of a substantial amount (potentially 50% or more) in SBRT compared to SR.

10.1.2 Secondary Endpoints

The secondary objective of this Phase III trial is to compare the time-to-locoregional recurrence using a standardized definition of locoregional recurrence to be applied to both arms. In brief, locoregional

recurrence will be defined as recurrence within the same lobe or hilum (N1 nodes), or within 2 cm of the staple line or within 2 cm of the PTV after treatment effects such as scarring have subsided. This will be a first attempt to set comparable locoregional recurrence definitions for these two different treatment modalities.

Other secondary endpoints are adverse events, disease-free survival, and pulmonary function. Adverse event rates will be compared at specific timepoints (1, 3, and 12 months post therapy). Disease-free survival is defined as the time from randomization until documented disease-recurrence or death, whichever occurs first. Patient who are disease-free and alive at the time of analysis will be censored at the time of their last follow-up. Patients will be followed for disease-free survival for a minimum of 5 years. Pulmonary function will be evaluated by PFTs and will be compared at specific timepoints as well as over the entire period of observation.

A tertiary aim of the study is to compare the adverse event rates and PFT values in each arm for patients with low or high Charlson comorbidity index scores, including a test interaction between Charlson Comorbidity Index scores (low vs. high) and treatment arm. If there a substantial interaction term, this index may potentially be used to select patients for SBRT or SR.

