1.3.2 Secondary Objectives

- To compare loco-regional recurrence-free survival between study arms. See Evaluation of Outcomes (Section 7) for recurrence definitions.
- To compare disease-free survival between study arms.
- To compare grade 3 or higher specific adverse event profiles between study arms; specific comparisons will include AEs at 1, 3, 6 and 12 months post therapy.
- To compare pulmonary function between patients treated with SBRT and patients treated with SR.
- To compare the adverse events and PFTs in each arm for patients with low or high Charlson comorbidity index scores, including a test interaction between Charlson comorbidity index scores (low vs. high) and treatment arm.

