7.2 Relapse/Progression Definitions

All patients will be assessed for disease relapse/progression. The types of local, regional and distant relapse/progression will be recorded to determine if there are differences in the pattern of relapse/progression between arms.

PET/CT is required to confirm disease relapse/progression (i.e., if CT scan alone is suspicious for relapse/progression, then PET/CT is required to confirm disease status). Biopsy confirmation of relapse is highly recommended but not required. When biopsy is feasible, the following methods are recommended: fine-needle aspiration biopsy, EBUS, EUS, VATS or open biopsy.

CT imaging at three months will be considered the new baseline to account for inflammatory changes and fibrosis after SBRT or SR. The table below describes the different areas defined as local, regional, and distant relapse/progression after treatment effects have subsided.

Type of Recurrence	Modality	Description (after treatment effects have subsided)		
Local Failure				
Primary tumor failure (PTF)	SBRT	Appearance of residual tumor located within the extent of the primary targeted tumor.		
Marginal failure (MF)	SR/SBRT	SR: Appearance of tumor ≤ 2 cm in any direction of the staple-line or the structures immediately adjacent to prior tumor site (chest wall/ mediastinum/ diaphragm/ spine).		
		SBRT: Appearance of tumor ≤ 2 cm in any direction of the primary tumor or structures immediately adjacent to primary tumor (lung/ chest wall, mediastinum/ diaphragm/ spine).		
Involved Lobe failure (ILF)	SR/SBRT	SR: Appearance of tumor > 2 cm in any direction of the staple-line.		
		SBRT: Appearance of tumor > 2 cm in any direction of the primary tumor.		
Port site/wound failure (PWF)	SR	Appearance of tumor at a port or incision site after VATS or open resection.		
Regional Failure				
Non-primary lobe failure (NLF)	SR/SBRT	Appearance of tumor within another ipsilateral (non- primary) lobe.		
Hilar nodal failure (HNF)	SR/SBRT	Appearance of tumor in ipsilateral hilar lymph nodes		
Ipsilateral mediastinal nodal failure (MNF)	SR/SBRT	Appearance of tumor in ipsilateral mediastinal and/or subcarinal lymph nodes.		
Distant Failure				
Distant nodal failure (DNF)	SR/SBRT	Appearance of tumor in ipsilateral supraclavicular or contralateral lymph nodes .		

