10.3.3 Secondary Endpoint Analyses

Local-regional recurrence-free survival and disease-free survival will be compared using a one-sided logrank test. As for the primary analysis, we will exclude patients who are randomized but then cancel and refuse the treatment to which they were assigned. We will also perform the fully intention to treat approach as a sensitivity analysis.

Analysis of the adverse event rates and PFT values will involve chi-square tests and t-tests and Wilcoxon procedures at each time point as well as a repeated measures analysis of variance (ANOVA) and general estimation equations (GEE) modeling using data from all timepoints. [126] Models will include covariates of patient characteristics as well as treatment arm to perform a conditional analysis of treatment comparison in the presence of potentially confounding variables. The extent of missing data will be explored for non-random influences. [127] Sensitivity analysis will be performed using various simple imputation techniques to ensure results are not unduly influenced by the presence of missing data. [128,129] We examine the impact of imputing using such methods as last-value-carried forward, nearest-neighbor imputation, zero-value imputation, minimum-value imputation, and maximum-value imputation on the result original analysis. The degree of variability in the results will allow for a calibration of the impact of the best and worst case scenarios in terms of patterns in the missing data on the stability of the analytical results.

A tertiary analysis is planned that will compare the adverse events and PFTs profiles in each arm for patients with low or high Charlson Comorbidity Index scores, including a test interaction between Charlson Comorbidity Index scores (low vs. high) and treatment arm. Again, we will use appropriate modeling techniques. Modeling techniques will also be used to determine other prognostic variables that might be used to determine other characteristics that are associated with outcome in the different treatment arms.

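### The locoregional secondary endpoint has two definitions that do not match, two names and no rule for death; separately, its one-sided test has no stated direction or alpha

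*Combined protocol and SAP*

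**What the plan says.** Section 1.3.2 sets the objective: "To compare loco-regional recurrence-free survival between study arms. See Evaluation of Outcomes (Section 7) for recurrence definitions". The table in Section 7.2 has four local rows (primary tumor, marginal, involved lobe, port or wound) and three regional rows (another ipsilateral lobe, ipsilateral hilar nodes, ipsilateral mediastinal or subcarinal nodes). Three rows matter here:

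- mediastinal nodes: "Appearance of tumor in ipsilateral mediastinal and/or subcarinal lymph nodes"
- other lobes: "Appearance of tumor within another ipsilateral" lobe
- the SR-only row: "Appearance of tumor at a port or incision site after VATS or open resection"

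For SBRT the table takes its 2 cm distance from the primary tumor.

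Section 10.1.2 names the endpoint as time to locoregional recurrence and offers a short definition: "recurrence will be defined as recurrence within the same lobe or hilum (N1 nodes), or within 2 cm of the staple line". For SBRT, the same distance is taken from the PTV instead of the staple line. The section defines disease-free survival with death as an event but gives no such rule for the locoregional endpoint.

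Section 10.3.3 gives the only analysis: "Local-regional recurrence-free survival and disease-free survival will be compared using a one-sided logrank test".

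**The concern.** Section 1.1 blames non-uniform recurrence definitions for the difficulty of comparing surgery with SBRT. It gives a shared definition as a reason for randomizing, and 10.1.2 presents its own as a first attempt at one. If the statistics section and the outcomes section classify the same patient differently, that purpose is weakened. Two of the differences also fall on one arm only: the PTV reference applies to SBRT, and port or wound failure to SR.

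The name matters as much as the list of sites. Time to locoregional recurrence and recurrence-free survival answer different questions in a high-risk population where deaths without recurrence are common. An analyst who must choose between them, or between the two lists of sites, after seeing the data can change the result.

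**Working it through.** The plan gives no sample size, event count, alpha or power for this endpoint, so there is no stated figure to reproduce.

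**Step 1. The two definitions side by side.**

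| Isolated first failure | Section 7.2 (local or regional) | Section 10.1.2 |
|---|---|---|
| Same lobe | event | event |
| Ipsilateral hilar nodes | event | event |
| Within 2 cm of staple line | event | event |
| Ipsilateral mediastinal or subcarinal nodes | event | not listed |
| Other ipsilateral lobe, outside the 2 cm zone | event | not listed |
| Port or incision site (SR) | event | not listed |

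The overlap is large, but three whole categories differ. Section 1.1 also treats mediastinal nodal recurrence as regional, which agrees with 7.2 and not with 10.1.2.

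**Step 2. The SBRT distance.** Section 5.3.4.1 expands the GTV by 0.5 cm axially and 1.0 cm craniocaudally to form the PTV. Two centimetres from the PTV is therefore 2.0 + 0.5 = 2.5 cm axially and 2.0 + 1.0 = 3.0 cm craniocaudally from the GTV, against 2.0 cm from the primary tumor in 7.2. This changes few classifications. Both texts count any same-lobe recurrence, and 7.2 counts other ipsilateral lobes as well. What is left is non-lung tissue roughly 2 to 3 cm from the tumor.

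**Step 3. How much the rule for death matters.** Inputs:

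- 3-year survival of 80% (Section 10.2), applied to both arms
- 3-year locoregional failure of 13%, from the 87% local-regional control quoted in Section 1.1 for RTOG 0236, an SBRT cohort of inoperable patients; this is an assumption for the present trial, so the range 5% to 17% is shown
- 400 patients, 40 months of uniform accrual, 42 months minimum follow-up (Section 10.2)
- independent exponential hazards (assumption)

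Cumulative 3-year hazards: death −ln(0.80) = 0.223; recurrence −ln(0.87) = 0.139.

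Death share of first events = 0.223 / (0.223 + 0.139) = 0.223 / 0.362 = 62%.

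Expected events = 400 × {1 − [exp(−λf) − exp(−λ(a + f))] / (λa)}, with λ = 0.362/3 per year, a = 40/12 and f = 3.5 years. This gives about 184 recurrence-or-death events, of which about 71 are recurrences.

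If SBRT multiplied only the recurrence hazard by 1.6, the composite hazard ratio would be (1.6 × 0.139 + 0.223) / 0.362 = 1.23.

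Approximate power at one-sided 5% (level assumed) is Φ(½√d · ln HR − 1.645), where d is the event count computed above without a treatment effect.

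| 3-year locoregional failure | Recurrences | Recurrence or death | Death share | Composite HR | Power, recurrence alone (HR 1.6) | Power, composite |
|---|---|---|---|---|---|---|
| 5% | 28 | 150 | 81% | 1.11 | 34% | 16% |
| 10% | 55 | 172 | 68% | 1.19 | 54% | 31% |
| 13% | 71 | 184 | 62% | 1.23 | 63% | 41% |
| 17% | 91 | 201 | 54% | 1.27 | 73% | 53% |

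The composite has more events but less power for a difference confined to recurrence.

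**Step 4. The test.** The primary analysis is one-sided against a stated margin of HR 1.6 at a stated level. Section 10.3.3 gives neither for the locoregional endpoint, nor says which arm is hypothesized to be better. Section 14.1 refers in passing to a non-inferiority design for recurrence as well as death, but no recurrence margin appears. This gap is the same whichever definition is followed.

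**The case against.** The best defence is that Section 7.2 governs. The objective says so ("See Evaluation of Outcomes (Section 7) for recurrence definitions"), and 10.1.2 announces itself as an abbreviated version. That is the most natural reading, and it is why the two texts are better called mismatched than irreconcilable. It does not remove the problem. A summary may shorten, but this one drops whole failure types and changes the structure from which distance is measured, and it sits in the section an analyst will follow.

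It is also fair to say that failure types are recorded by category, so either composite could be rebuilt. That stands; it makes the repair cheap, but does not say which composite is the planned one.

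On direction, the plan is not wholly silent. Section 1.2 expects a lower chance of complete local control with SBRT than with resection. Section 1.1, however, expects recurrence rates to differ without naming the better arm, and 10.3.3 does not turn either statement into a hypothesis.

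A reader might infer that mediastinal failure is where the arms must differ because only surgery samples nodes. The documents do not support this. Section 2.1 requires clinically suspicious nodes to be confirmed negative before registration in both arms, Section 5.1 recommends but does not require sampling at surgery, and Section 1.1 says only that regional rates may possibly differ.

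**Conclusion.** The inconsistency is established by the text: two lists of qualifying sites, two endpoint names with one analysis between them, and no rule for death. Unstated direction, alpha and margin for the one-sided test are a separate omission. It should be corrected before analysis, but it touches a secondary endpoint only.

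Three stronger readings should be resisted.

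- A reader might infer that two endpoints are each analysed. Only recurrence-free survival has a method, and that death is not an event under the other name is an inference from the name.
- A reader might take (13 − 9)/13 = 31%, from the 91% local and 87% local-regional control quoted for RTOG 0236, as the share of failures that 10.1.2 drops. That share includes hilar failures, which 10.1.2 keeps, so it is at most an upper bound for the omitted regional failures. The 4-point difference in 55 patients is about 0.04 × 55 = 2 people.
- A reader might infer that recurrence-free survival would simply repeat overall survival. At 62% deaths, about 38% of first events are still recurrences. The figure pairs inoperable SBRT patients' recurrence with an SR survival assumption and treats the two hazards as independent. It shows dilution, not duplication.

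**What to change.** 1. Replace the definition in 10.1.2 with a cross-reference to all Local and Regional rows of the Section 7.2 table, and use one SBRT distance reference throughout.
2. Choose one endpoint and use its name in 1.3.2, 10.1.2 and 10.3.3. If it is time to locoregional recurrence, treat death as a competing event and report cumulative incidence with a cause-specific hazard ratio. If it is recurrence-free survival, count death as an event and also report locoregional recurrence alone. Either way, state what happens when distant failure comes first, since Section 6.2 follows patients after relapse for survival and quality of life.
3. For this endpoint and disease-free survival, use a two-sided 5% test with hazard ratio and 95% confidence interval. Alternatively, keep the one-sided test and state its direction and alpha, and its margin if non-inferiority is meant.

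The cost is protocol and SAP wording; failure types are already recorded. If the one-sided level would have been 5%, a two-sided test raises the critical value from 1.645 to 1.960. With 71 recurrences and a hazard ratio of 1.6, approximate power falls from 63% to 51%. The primary analysis and sample size do not change.

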10.2 Sample Size

This is a non-inferiority trial designed to determine whether the overall survival rate for SBRT is clinically (and statistically significantly) no worse than the overall survival for SR. We used published survival rates from the literature for SR in this patient population [2, 8, 19, 103]. The 3-year survival rate for SR (control group) appears to be approximately 80%. We will deem SBRT as non-inferior to SR if the 3 year overall survival rate for SBRT is no more than 0.10 less than that for SR. In other words, if the survival rate for SBRT at 3 years is more than 0.10 less than that for SR. In other words, if the survival rate for SBRT at 3 years is more than 0.10 less than the 3 year survival rate for SR, we will declare SBRT to be an inferior treatment compared to SR in terms of overall survival. To power the study, we assumed an exponential distribution for the survival rate and a HR of 1.60 (which reflects a 10% 3-year survival rate for SR is at least 0.10 greater than that for SBRT (0.80 for SR versus 0.70, or less, for SBRT). The alternative hypothesis is that the HR is 1.00 or that the 3 year survival rate for SR compared to SBRT is no more than 0.10. If we reject the null hypothesis, we will assume the two treatments are equivalent with respect to overall survival, if we do not reject the null hypothesis, we will assume that SR is superior to SBRT is no more than 0.10.

To determine the sample size for the trial we assumed a significance level of 0.05, an HR of 1.60 (SBRT versus SR, for the null hypothesis) and set power to be 90%. We plan a single interim analysis when half of the expected events (deaths) have occurred; this will be for futility only. Assuming a 3-year survival rate of 0.80, a HR of 1.60 yields a 3-year survival rate for SBRT of 0.70 or less for the null hypothesis. Assuming an accrual rate of 10 patients per month, an expected accrual duration of 40 months (3 1/3 years), and a minimum follow-up of 42 months (3.5 years), the necessary sample size is 400 eligible patients (200 per arm). To ensure that there is an adequate number of eligible patients (including patient refusals after randomization and prior to treatment), we will have a target accrual that is approximately 5% greater than this or 420 patients. This trial is expected to accrue in approximately 40 months and the final analysis will occur after 166 deaths have been observed or about 82 months (6.8 years) after the first patient is enrolled.

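### The Charlson-by-arm interaction is planned on a low/high split with no cut-point: power is lost if the effect is graded, and the cut could still be chosen from the data

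*Combined protocol and SAP*

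**What the plan says.** The same analysis appears three times in the combined protocol and SAP.

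- Section 1.3.2 lists it among the secondary objectives: "To compare the adverse events and PFTs in each arm for patients with low or high Charlson comorbidity index scores".
- Section 10.1.2 calls it a tertiary aim: to "compare the adverse event rates and PFT values in each arm for patients with low or high Charlson comorbidity index scores", again with an interaction test.
- Section 10.3.3 calls it a tertiary analysis of adverse event and PFT profiles, "including a test interaction between Charlson Comorbidity Index scores (low vs. high) and treatment arm".

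On method, 10.3.3 says only: "Again, we will use appropriate modeling techniques". On use of the result, 10.1.2 begins a condition with "If there a substantial interaction term" and concludes that "this index may potentially be used to select patients for SBRT or SR".

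No section defines low or high, gives a rule for setting the cut, states a significance level for the interaction, or says what size would count as substantial. The Study Calendar (Section 3) collects the index after registration and before treatment, so the full score should be available at baseline. It is not a stratification factor (4.1).

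**The concern.** Two features of the plan combine. First, a score recorded in full is reduced to two groups for the test, which discards information whenever the treatment difference changes gradually with comorbidity. The trial is sized for overall survival (10.2), and no power is stated for this interaction, so the loss falls on a test that was never powered.

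Second, the dividing point is left open. An analyst could settle it after seeing which split looks most striking. By contrast, the patient-reported outcome study in 14.1 fixes its deficit cut in advance, at 5 or less on a 0-10 scale.

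At stake is a possible basis for directing patients to surgery or radiation. A real interaction could be missed, or a chance one could be taken up.

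**Working it through.** The plan gives no power, effect size or significance level for this interaction, so there is no stated figure to reproduce. The check asks what the split costs and what an open cut could do.

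**Inputs from the documents.** 400 eligible patients, 200 per arm (10.2). For adverse events, the 30-day grade 3+ rate in the two Z4032 arms (1.1) pools to (29 + 33)/(114 + 109) = 62/223 = 28%. The SBRT rate is set to half of that, 14%, following the expectation in 10.1.1.

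**Assumptions.** Two-sided 5% test. The Charlson distribution is not given, so four were tried: Poisson with mean 1, 2 and 3, and negative binomial with mean 2 and variance 4. Cuts leaving 10-90% of patients in the high group were examined, with 4,000 simulated trials per setting.

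**Power, continuous outcome (PFT).** With 1:1 allocation, a score standardised to SD 1 and outcome SD 1, the standard error of the interaction slope is 2/√400 = 0.10. A slope of 0.28 then gives z = 2.80 and power Φ(2.80 − 1.96) = Φ(0.84) = 80%. If the score is replaced by a split whose squared correlation with it is r², the expected z shrinks to 2.80√r², and power is about Φ(2.80√r² − 1.96).

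| Assumed distribution | Score, simulated | Best cut: r², formula, simulated | Worst cut: r², formula, simulated |
|---|---|---|---|
| Poisson 1 | 80% | ≥2: 0.70, 65%, 64% | ≥1: 0.58, 57%, 56% |
| Poisson 2 | 80% | ≥3: 0.67, 63%, 63% | ≥1: 0.31, 34%, 35% |
| Poisson 3 | 80% | ≥4: 0.66, 62%, 62% | ≥2: 0.42, 44%, 45% |
| Neg. binomial 2 | 79% | ≥3: 0.65, 62%, 61% | ≥1: 0.33, 36%, 37% |

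Formula and simulation agree to about one point. The best split uses the information of 0.65 × 400 = 260 to 0.70 × 400 = 280 patients.

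**Type I error, no true interaction.**

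- Score as a linear term (PFT): 4.7-5.2%.
- Any one cut fixed in advance (PFT and adverse events): 4.5-5.8%. The simulation standard error is √(0.05 × 0.95/4000) = 0.3 points, so this is close to nominal.
- Most significant of the candidate cuts:

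| Assumed distribution | Cuts tried | PFT | Adverse events |
|---|---|---|---|
| Poisson 1 | 2 | 9% | 10% |
| Poisson 2 | 4 | 16% | 16% |
| Poisson 3 | 4 | 16% | 16% |
| Neg. binomial 2 | 5 | 18% | 19% |

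For comparison, independent tests would give 1 − 0.95² = 9.8% for two and 1 − 0.95⁴ = 18.5% for four.

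The adverse event runs tested the difference in risk differences and cover type I error only. No power figure was computed for that outcome.

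**The case against.** A reader might infer that the plan, as written, inflates false positives. The documents do not support that. In randomised arms a single split chosen without sight of outcomes holds its level. Inflation needs a cut picked from the outcome data, or several cuts tried, and no section plans either. What stands is that nothing rules it out.

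A reader might also infer that the index is intended to decide who gets which treatment. Section 10.1.2 is conditional and tentative, and no decision within this trial depends on the result. The statistical sections rank the analysis as tertiary; citing only the secondary label in 1.3.2 would overstate its weight.

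On power, simulating a linear interaction favours the linear test. If the true effect were a step at the chosen cut, the split would lose nothing. This is correct and limits the claim, but the plan names no threshold and gives no reason to expect one.

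Finally, comparing two groups is a natural way to describe adverse events and PFTs by comorbidity, and the unspecified modelling in 10.3.3 does not exclude a continuous term. The descriptive use is fair and can stay. But all three statements of the interaction test specify low versus high, so the continuous form is at best permitted, not planned.

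**Conclusion.** The point holds in a limited form. The plan commits the arm-by-Charlson test to a two-level split and fixes no cut. If the interaction is graded in the score, about 80% power falls to 61-64% at the best cut and to about 35% at a poor one. If the effect is a threshold at the chosen cut, there is no such loss. The open cut is a vulnerability, not a demonstrated error: type I error stays near 5% with one pre-fixed cut and reaches about 9-19% only if the best of two to five cuts is reported.

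These figures are illustrative ranges. They rest on assumed score distributions, a two-sided 5% level and, for power, a linear interaction on a continuous outcome. The survival comparison is unaffected.

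**What to change.** In 10.1.2 and 10.3.3, define the interaction test as arm by Charlson score, with the score entered as a number in a single linear term. Prespecify a spline version as a sensitivity check only, so that it cannot replace the main test after the fact.

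Keep the low/high grouping for descriptive tables, with one numeric cut written into the plan now. A median taken later from accrued data would not be a safeguard: the documents describe no blinding, and under 10.4 the study chair and statistician review toxicity and endpoints twice a year.

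Label the result exploratory in 1.3.2, 10.1.2 and 10.3.3, which would also remove the mismatch between secondary and tertiary.

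The cost is wording: no new data and no more patients. The downside is that the test assumes a roughly linear trend on the scale of the model used, and would be less sensitive to a sharp threshold.
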